#### **Key exclusion criteria include**

- Renal or hepatic transplantation (prior or planned within the study period)
- Plasma oxalate (Pox)  $> 30 \text{ } \mu\text{mol/L}$  at Screening
- Documented evidence of clinical manifestations of severe systemic oxalosis (including preexisting retinal, heart, or skin calcifications, or history of severe bone pain, pathological fractures, or bone deformations)

**Number of Participants:** Approximately 25 participants will be enrolled such that approximately 20 participants (approximately 7 aged 6 to 11 years; approximately 10 aged 1 to

[figure not shown]
5 years; and approximately 3 aged < 1 year) complete the study, with an overall goal of approximately 15 PH1.

**Intervention Groups and Duration of Participation:** This study has a single intervention group in which all participants will receive monthly SC doses of nedosiran over a 6-month period. Prospective participants will be screened over an up-to-35-day period, with an extra 14 days allowed for participants who are required to repeat initially unanalyzable screening laboratory assessment samples. The total time on study for each participant is approximately 7 months.

**Study Duration:** Approximately 24 months from the first participant, first visit, to the last participant, last visit.

**Safety Review Committee:** This study will utilize an SRC to review safety and efficacy data on a periodic basis.

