## **7.2. Participant Discontinuation/Withdrawal from the Study**

The participant's parent or legal guardian has the right to withdraw permission (consent) at any time during the study or the participant may be withdrawn at any time at the discretion of the Investigator for safety, behavioral, compliance, or administrative reasons.

At the time of discontinuing from the study, if possible, an early discontinuation visit should be conducted, as shown in the SoA. See SoA (Section 1.3) for data to be collected at the time of study discontinuation and follow-up and for any further evaluations that need to be completed.

The participant will be permanently discontinued both from the study intervention and from the study at that time.

If the participant's parent or legal guardian withdraws consent for disclosure of future information, the Sponsor may retain and continue to use any data collected before such a withdrawal of consent.

If a participant withdraws from the study, the participant or participant's parent or legal guardian may request destruction of any samples taken and not tested, and the Investigator must document this in the site study records.

The reason for participant discontinuation or withdrawal from the study will be recorded on the eCRF. Participants who sign the ICF but do not receive the study intervention may be replaced. Participants who sign the ICF and receive the study intervention, and subsequently withdraw, or are withdrawn or discontinued from the study may be replaced at the discretion of the Sponsor.

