1.1.2 Primary Estimand

The primary clinical question of interest is: What is the treatment effect of nedosiran in lowering urinary oxalate excretion (Uox) assessed via percent change from baseline in spot urinary oxalate-to-creatinine ratio at Month 6 in PH1 pediatric participants (birth to 11 years of age) with relatively intact renal function.

For the primary objective, the estimand is defined with five attributes:

- Treatment condition of interest is the monthly nedosiran administration.
- The target population is PH1 pediatric participants (birth to 11 years of age) with relatively intact renal function.
- The endpoint is percent change from baseline at Month 6 in spot urinary oxalate-to-creatinine ratio.
- The intercurrent events (ICEs) include treatment discontinuation for any reasons and will be handled by the treatment policy strategy.

[figure not shown]
Population-level summary is the percent change from baseline at Month 6 estimated by Mixed-effect Model Repeated Measures (MMRM) approach.

Rationale for estimand: The primary estimand assesses the treatment benefit of nedosiran in lowering urinary oxalate-to-creatinine ratio that can be expected in clinical practice, provided that the treatment adherence in the study reflects what would be seen in clinical practice.

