4.1.1.3 Handling of Dropouts or Missing Data

4.1.1.3.1 Missing Efficacy Endpoint Data

While all possible efforts will be made to ensure that participants stay in the study and all data is collected as scheduled, the occurrence of missing data cannot be eliminated.

Participants who sign the informed consent form but do not receive the study intervention may be replaced. Should there be a participant(s) who signs the informed consent form, and receives the study intervention and subsequently withdraws, or is withdrawn or discontinued from the study before the Day 180 Visit, an additional participant(s) in the same age group may be enrolled to ensure that an adequate number of participants complete the Day 180 visit assessments.

No other imputation will be used in the study except for partial dates described in Section [4.1.1.7](#).

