4.2.2 Main Analytical Approach

The primary analysis of the primary endpoint will be performed for MITT using a restricted maximum likelihood (REML) based MMRM approach with percent change from baseline at scheduled visits (Month 1 – Month 6) as the dependent variable. Analysis will include fixed effects of scheduled visits, baseline spot urinary oxalate-to-creatinine ratio, baseline age and baseline eGFR. Denominator degrees of freedom for the F-test for fixed effects will be estimated using the Kenward-Roger approximation. A compound symmetry (CS) covariance structure will be used to model the within-patient error given the small sample size for this study. The primary estimate is the least square (LS) mean of the percent change from baseline at Month 6. This LS mean will be presented along with corresponding standard errors (SEMs) and 95% confidence intervals (CI). Similar analysis will be performed to estimate the LS mean of the percent change from baseline averaged over Month 3 to Month 6.

Descriptive summary statistics (n, mean, standard deviation, median, minimum, maximum) for MITT population by PH type and by age group (0-<2, 2 - < 6, 6-<9, and 9 - 11 years) will also be provided.

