4.2.3 Sensitivity Analyses

As sensitivity analyses, the same analyses as described in Section 4.2.2 will be performed for the EVAL population and PP population. Also, the same analyses as described in Section 4.2.2 will be performed by imputing creatinine measurements or urine oxalate values reported as '<x' where x is the lower limit of quantification (LLOQ) value.

Similar analyses will be performed for absolute change from baseline at Month 6 and averaged over Month 3 to Month 6 in spot urinary oxalate-to-creatinine ratio for MITT population, EVAL population, and PP population.

To further adjust for the any potential confounding effect of natural maturity on spot urinary oxalate-to-creatinine ratio, similar analyses will be performed on the ratio of spot urinary oxalate-to-creatinine ratio to the ULN tailored to individual patient's age for MITT population, EVAL population, and PP population.

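### For children who leave the study, the Month 6 model assumes a largely on-drug response under a treatment-policy estimand, and no planned sensitivity analysis varies that assumption

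*SAP*

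**What the plan says.** **Estimand.** SAP 1.1.2 states: "The intercurrent events (ICEs) include treatment discontinuation for any reasons and will be handled by the treatment policy strategy". It adds: "Population-level summary is the percent change from baseline at Month 6 estimated by Mixed-effect Model Repeated Measures (MMRM) approach". It gives no separate rule for withdrawal from the study.

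**Model.** SAP 4.2.2 specifies a "restricted maximum likelihood (REML) based MMRM approach with percent change from baseline at scheduled visits" from Month 1 to Month 6. The fixed effects are visit, baseline ratio, baseline age and baseline eGFR, with a compound-symmetry covariance. There is no term for being on or off drug.

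**Missing data.** SAP 4.1.1.3.1 allows dosed children who leave to be replaced, then says: "No other imputation will be used in the study except for partial dates described in Section" 4.1.1.7.

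**Stopping drug versus leaving.** Protocol 7.1.1 says that stopping the drug is not leaving the study and that the remaining visits should be completed. On withdrawal from the study, Protocol 7.2 says: "The participant will be permanently discontinued both from the study intervention and from the study at that time". An early discontinuation visit is to be held if possible, and Protocol Table 1 includes spot urine at that visit. SAP 4.1.1.5 maps an early-termination value to the next scheduled visit if it falls 20 to 40 days after the last one.

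**Sensitivity analyses.** SAP 4.2.3 says "the same analyses as described in Section 4.2.2 will be performed for the EVAL population and PP population". It adds a run with values below the quantification limit imputed, one on absolute change, and one on the ratio to the age-specific ULN.

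**The concern.** Under a treatment policy strategy, a child's Month 6 value counts whether or not the child still takes nedosiran. For a child who has left, that value usually does not exist. A likelihood-based model under missing-at-random then stands in for it, using the child's own earlier values and the children still followed. Both sources are mostly on-drug, so for leavers the estimate answers something close to what would have happened on continued treatment.

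This matters because the study has one arm. The Month 6 LS mean and its interval are the primary efficacy result, and no control group absorbs a shift. The shift is in the favourable direction. Protocol 9.4 promised that the SAP would set out how missing data are handled, but the SAP offers replacement of participants and a no-imputation rule. None of the analyses in SAP 4.2.3 changes the missing-data assumption. EVAL requires six full doses and completion of Day 180, so it removes every leaver. Agreement between EVAL and the main analysis would therefore say nothing about leavers.

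**Working it through.** **The plan's own figures.** There is no formal sample size and no stated dropout rate, effect size or SD. The synopsis says: "Approximately 25 participants will be enrolled such that approximately 20 participants" complete (7 + 10 + 3 = 20 by age group). Read literally, 1 - 20/25 = 20% do not complete. But Protocol 4.1, Protocol 9.2 and SAP Section 5 say that about 25 are *screened*. On that reading the 25 include screen failures, and loss after dosing could be anywhere from 0 to 20%. The closest attrition figure in the documents is the earlier 6-month study in Protocol 2.2.3.1, where 33 of 35 completed study treatment: 2/35 = 5.7% lost.

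**Formula.** Let E be the on-drug change at Month 6, d the share leaving after dosing, and r the share of E that leavers keep at Month 6. If leavers responded like the others while on drug:
- the model estimates about E;
- the treatment-policy value is (1-d)E + d·r·E = E[1 - d(1-r)];
- the overstatement is d(1-r) of the headline.

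**Results.**
- d = 5.7%, full loss (r = 0): 5.7%. Half loss (r = 0.5): 2.9%.
- d = 10%: 10% and 5%.
- d = 20%: 20% and 10%. The 20% is 0.20/0.80 = 25% of the true effect: same gap, smaller denominator.
- d = 0 or r = 1: 0.
- One fully reverting leaver among 25 children: 1/25 = 4%. Among 15: 1/15 = 6.7%.

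**Simulation check.** Random-intercept REML model with visit effects, 200 runs per scenario. Assumed: E = -50%, between- and within-child SD 15 points each, N = 25, last on-drug month uniform on 1 to 5, linear waning to Month 6.

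| Scenario | Estimate | True | Overstatement, % of headline |
|---|---|---|---|
| 5 leave, full loss, no early-termination value | -50.5 | -40.0 | 20.7 |
| Same, early-termination value mapped | -47.5 | -40.0 | 15.8 |
| 5 leave, half loss | -49.8 | -45.0 | 9.6 |
| Same, early-termination value mapped | -48.9 | -45.0 | 8.0 |
| 5 leave, half-responders on drug, full loss | -46.9 | -40.0 | 14.7 |
| 2 leave, full loss | -50.2 | -46.0 | 8.4 |
| 1 leaves, full loss | -50.2 | -48.0 | 4.3 |
| 5 stop drug but stay, full loss | -40.0 | -40.0 | 0.1 |

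The formula holds, and the last row confines the problem to children who leave the study.

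**Scale for any imputation.** The eligibility cut-offs in Protocol 5.1 fall with age: 0.44 below 6 months, 0.34 from 6 to under 12 months, 0.26 from 12 months to under 2 years. Crossing one boundary lowers the cut-off by 1 - 0.34/0.44 = 23% or 1 - 0.26/0.34 = 24%. Zero change in the raw ratio is therefore not an untreated Month 6 value for an infant.

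**The case against.** **The loss may be small.** At 2 of 35 and an assumed -60% effect, the shift is 0.057 × 60 = 3.4 points under full loss and 1.7 under half loss. With assumed SDs of 20 and 20 and N = 25, the Month 6 standard error is about √(400+400)/5 = 5.7 points, a 95% half-width of about 11 to 12. The analysis is descriptive, with no confirmatory test. This stands, and it limits the point to a moderate one. The shift is nevertheless systematic, and the interval does not cover it.

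**Full loss in every leaver is unlikely.** Doses fall on Days 1, 30, 60, 90, 120 and 150. A child last seen at Month 5 and dosed then has had all six. Protocol 2.2.3.1 reports a mean 24.5% decrease at Day 85 after one dose in PH3. This stands: full loss is a bound, not an expectation.

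**Early-termination urine is collected.** This stands in part. The mapping fills Month 6 only for a child last seen at Month 5. For earlier leavers it fills an intermediate visit and Month 6 stays missing.

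**The SAP qualifies its claim.** SAP 1.1.2 makes relevance to practice conditional on similar adherence. That condition concerns how far adherence carries over to practice. It does not turn a leaver's predicted on-drug value into a treatment-policy value.

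**Stronger readings the documents do not support.** A reader might infer that every child who stops nedosiran is analysed as if still treated. Protocol 7.1.1 keeps such children in follow-up, and their off-drug values are used as long as the urine is collected. A reader might also infer that PP excludes leavers, as EVAL does. SAP Section 3 defines PP by major deviations affecting efficacy assessment and does not list withdrawal as one.

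**Conclusion.** The point holds for children who leave the study. For them the estimator leans towards a hypothetical strategy while the estimand says treatment policy, and nothing in SAP 4.2.3 tests the difference.

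The size depends on two quantities that the plan does not give. If post-dose loss resembles the earlier 6-month study and leavers lose half to all of the effect, the headline reduction is overstated by about 3% to 6% of itself. It is zero if nobody leaves or the effect lasts to Month 6.

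A reader might take 20% as the expected bias from the 25-to-20 figures. The documents do not support that. It needs all five losses to occur after dosing, complete loss of effect in each, and no mapped early-termination value. It is the worst case on the planned numbers. It is not a formal ceiling, since dosed children who leave may be replaced. What is affected is the point estimate and its interval, not an error rate.

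One related inconsistency bears on how many children leave. For participants under 6 years, Protocol 10.6 sends some liver-related stops to discontinuation from the study, whereas Protocol 7.1.1 says that stopping the drug does not mean leaving it. These passages must be reconciled.

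**What to change.** **SAP 4.2.3.** Add one prespecified sensitivity analysis on the primary analysis set:
- Keep all observed values and any early-termination values mapped under SAP 4.1.1.5.
- For visits missing after a child has stopped drug and left the study, use multiple imputation that moves the child back towards baseline on the age-specific ratio-to-ULN scale. Convert back to the raw ratio before computing percent change.
- Run it over a range from no loss to full loss of effect (for example r = 1, 0.5 and 0). Label full return as the conservative bound.
- Keep missing-at-random for visits missed intermittently.
- Report the Month 6 LS mean and 95% CI beside the main result.

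**SAP 4.1.1.3.1.** Permit this imputation. The section needs an edit in any case, because SAP 4.2.3 already imputes values below the quantification limit.

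**SAP 1.1.2.** State that, for children who leave the study, the main model assumes continued on-drug response after their last observed value.

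**Cost.** SAP wording and one extra analysis run, with no new data. The added figure will be less favourable than the headline, and conservative if the effect outlasts dosing. If nobody leaves, it changes nothing.

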1.2 Study Design

This is a Phase 2, multi-dose (3.5 mg/kg, not to exceed 170 mg), open-label, single-arm uncontrolled multi-center study of nedosiran in pediatric participants (birth to 11 years of age) with genetically confirmed PH1, PH2, or PH3, with relatively intact renal function based upon eGFR and serum creatinine.

Figure 1: Schematic design of trial

2 Statistical Hypotheses

No confirmatory testing will be done in this study.

2.1 Multiplicity Adjustment

Not applicable.

3 Analysis Sets

The following analysis populations are planned for this study:

Participant Analysis Set	Description
Safety Population (SAF)	
The safety population includes all participants who received at least 1 dose of study intervention.
Modified Intent-To-Treat Population (MITT)	
The MITT population includes all participants who received at least 1 dose of study intervention and have at least 1 post-baseline spot urinary oxalate to creatinine ratio. The MITT population is for efficacy analysis.
Evaluable Population (EVAL)	
The evaluable population includes all participants in the MITT population who received 6 full doses of study intervention and completed through the Day 180 Study Visit.
Pharmacokinetic Population (PK)	
The PK population will be defined in PK analysis plan (PKAP).
Per-Protocol Population (PP)	
The PP population includes all PH1 participants who received at least 1 dose of study intervention and had no major protocol deviations that affect efficacy endpoint assessment as adjudicated by the sponsor.
Interim Analysis Population	
The Interim Analysis population includes first 15 PH1 participants who completed the study.

4 Statistical Analyses

4.1 General Considerations

4.1.1 General Considerations for Analyses

4.1.1.1 Study Day

Study Day 1 is defined as the first dose date (i.e., date of first administration of study intervention). The first dose date is used as the reference start date for analysis.

For days prior to Study Day 1, Study Day = reference date – first dose date.

For days on or following Study Day 1, Study Day = reference date – first dose date + 1.

4.1.1.2 Baseline

For all endpoints (except spot urinary oxalate-to-creatinine ratio and annualized stone events rate), the last non-missing observation recorded prior to the first dose of study intervention will be used as the baseline observation for all calculations of change from baseline.

For assessments where the time is not collected (like QoL questionnaires), the last observation recorded prior or during the day of the first dose will be considered as baseline.

For spot urinary oxalate-to-creatinine ratio (including spot urinary oxalate and creatinine measurements), the average of all available spot urine samples (retest samples will be used if available) collected at screening will be used as baseline value.

For annualized stone events rate, baseline will be the number of stone events observed over the past 12 months prior to screening.

Any measure assessed after the date/time of the first dose will be considered as post baseline assessments.

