b In order to minimize blood loss in participants, samples to be drawn for screening should be collected not less than 28 days prior to samples drawn on Day 1.

c Visits for Days 2, 60, 120, and 150 may be conducted at the clinic or as at-home telehealth visits. During at-home telehealth visits, home-health nurses will collect the required blood and urine samples and perform an assessment of vital signs. The Investigator will contact the participant's caregiver via telephone and/or video conference to assess the general well-being of the participant and determine if any adverse events have occurred. The Investigator must affirm that nedosiran may be administered prior to administration.

d The Investigator will contact the participant's caregiver via telephone and/or video conference to assess the general well-being of the participant and determine if any adverse events have occurred.

e After the first 2 injections of nedosiran, visiting nurses or caregivers will administer SC injections at home for those months at which a study-site visit is not required. The total dose will be based upon body weight recorded on study Day 1. For participants < 6 months of age at Screening, the dose will be adjusted at Day 90 to capture changes in weight; no other dose adjustments are allowed.

f Parental informed consent (and minor assent, if applicable per local regulations) is required prior to initiation of screening procedures.

g Participant eligibility (with the exception of clinical laboratory testing) will be re-confirmed prior to administration of study intervention on Day 1.

h PH history to include 12-month history of stone events, or as applicable for those less than 12 months of age (Section 8.1.3).

i To include vitamin B6 (pyridoxine), if applicable.

j Participants without documented genotyping must provide a DNA sample for testing. For participants who weigh ≤ 11 kg, PH genotyping will be performed via buccal swab; for all other participants, while genotyping via buccal swab is recommended to reduce blood sample volumes, genotyping performed via whole blood sample is allowed.

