#### 8.1.3.1. Kidney Stone Events and Stone Burden

Parents or legal guardians of participants will provide a 12-month history of stone events (or as applicable for those less than 12 months of age) experienced by the participant at Screening and will report any stone events during the study.

For the purpose of this study, “stone events” are all events that meet one or more of the following criteria:

- **Renal stone requiring medical intervention** (e.g., outpatient procedures such as lithotripsy, or hospitalization and/or inpatient surgical intervention for confirmed stone related pain and/or complications)
- **Stone passage with or without hematuria**
- **Renal colic requiring medication**

Concurrent events will be defined as events occurring within the same 4-week (28-day) window.

Note: Although a change from baseline in the rate of stone events is an efficacy endpoint, stone events will be considered AESIs (Section [10.4.3](#)).

For the purpose of the study, “stone burden” is a term used primarily as a metric for quantifying and qualifying changes from baseline in the overall number and 2-dimensional surface area of renal stones, as observed via kidney ultrasound over the course of the study.

Taken together, the terms stone event and stone burden will be used to derive meaningful quantification and qualification of overall impact of clinical sequelae of renal stones during the course of the trial.

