4.1.1.6 Derived Variables

- Change from baseline = value at current time point – baseline value
- Percentage change from baseline = $\left(\frac{\text{value at current time point} - \text{baseline value}}{\text{baseline value}} \right) * 100\%$
- Spot urinary oxalate-to-creatinine ratio = the average of all the spot urinary oxalate-to-creatinine ratio collected at the specific visit.
- Treatment-emergent AE (TEAE) = any AE with an onset date/time on or after administration (including any partial administration) of the first dose of study intervention and until the study completion date from the end of study CRF.
- Body surface area will be calculated using the following formula (DuBois & DuBois, 1916):
$$BSA = (\text{Weight}^{0.425} \times \text{Height}^{0.725}) \times 0.007184;$$
 with weight in kilograms and height in centimeters.
- Body mass index (BMI) will be calculated using the formula: $\text{Weight [kg]} / (\text{Height}^2 [\text{m}^2])$.
- Estimated Glomerular Filtration Rate (eGFR) will be calculated as described in Protocol Section 8.2.6.1.
- Annualized stone event rate will be derived as number of stone events in the exposure period / total number of years exposed.

The number of stone events will be calculated as the number of discrete (non-concurrent) adverse events marked as a Kidney Stone Event on the adverse event CRF. Kidney stone events include renal stone requiring medical intervention, stone passage with or without hematuria, and renal colic requiring medication.

Concurrent events will be defined as events occurring within the same 4-week (28-day) window. For example, renal colic treated with medication on Monday 12 November 2019 followed by stone passage without hematuria on Friday 30 November 2019 is a single (concurrent) stone event (18 days between start and stop of single stone event). Renal colic treated with medication on Monday 12 November 2019 followed by stone passage without hematuria on Wednesday 13 December 2019 is considered two separate stone events (30 days between discrete event one and event two).

- Quality-of-life Questionnaires:

PedsQL

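### The SAP uses a raw 12-month stone count as an annualized baseline rate, which is too low for infants who have a prior event and less than 12 months of history

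*SAP*

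**What the plan says.** Change from baseline in annualized stone event rate is an exploratory endpoint (Protocol Section 3; SAP 1.1.1). SAP 4.4 summarizes it descriptively by PH type and age group, and the youngest age group is 0-<2 years.

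The two terms of the change are defined in different places:

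- **Baseline** (SAP 4.1.1.2): "For annualized stone events rate, baseline will be the number of stone events observed over the past 12 months prior to screening". The same section takes this endpoint out of the general baseline rule, so this sentence is the operative definition.
- **On study** (SAP 4.1.1.6): "Annualized stone event rate will be derived as number of stone events in the exposure period / total number of years exposed". The numerator is the "number of discrete (non-concurrent) adverse events marked as a Kidney Stone Event on the adverse event CRF", and "Concurrent events will be defined as events occurring within the same 4-week (28-day) window".

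Protocol 8.1.3.1 asks for a 12-month stone history at Screening, "or as applicable for those less than 12 months of age". Footnote h of the Schedule of Activities says the same: "PH history to include 12-month history of stone events, or as applicable for those less than 12 months of age". The SAP does not carry this allowance into its baseline definition, and SAP 4.8 records no change to protocol-planned analyses.

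**The concern.** For an infant, the rule subtracts a count that has not been annualized from a rate that has. The protocol recognizes that infants have a shorter look-back; the SAP derivation does not.

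The study is single-arm and uncontrolled, so change from baseline is its only comparison for stone events. Stone events are also adverse events of special interest (Protocol 10.4.3.1). An apparent rise in the youngest children that comes only from the derivation could be read as lack of effect or as a safety signal. Because results are reported by age group, the error falls in a small group, where a few participants can move the mean.

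**Working it through.** **Inputs**

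- Baseline as written: the count, with no divisor (SAP 4.1.1.2).
- On-study rate: events divided by years exposed (SAP 4.1.1.6). Day 180 gives 180/365.25 = 0.493 year, so one event is 2.03 per year and two are 4.06 per year.
- Planned completers: about 7 aged 6 to 11 years, 10 aged 1 to 5 years and 3 under 1 year, about 20 in all (Protocol synopsis).
- Stone event rate: the documents give none. Rates of 0.5 to 4 per year are assumed below.

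**Step 1: size of the understatement.** With m months of history, the annualized baseline is count/(m/12). The written baseline is the count, so it is too low by a factor of 12/m.

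**Step 2: expected spurious change.** With a constant true rate L, the expected history count is L × m/12 and the expected on-study rate is L. The written rule therefore gives L − L × m/12 = L × (1 − m/12) when nothing has changed.

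| Age at screening (months) | Factor 12/m | Spurious change, L = 1/yr | L = 2/yr | L = 4/yr |
|---|---|---|---|---|
| 1 | 12 | +0.92 | +1.83 | +3.67 |
| 3 | 4 | +0.75 | +1.50 | +3.00 |
| 6 | 2 | +0.50 | +1.00 | +2.00 |
| 9 | 1.33 | +0.25 | +0.50 | +1.00 |
| 12 or more | 1 | 0 | 0 | 0 |

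**Step 3: individual cases**

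- Age 6 months, one history event, one on study: as written 2.03 − 1 = +1.03; annualized 2.03 − 1/0.5 = +0.03.
- Age 6 months, two and two: as written 4.06 − 2 = +2.06; annualized 4.06 − 2/0.5 = +0.06.
- Age 4 months, one history event, one in half a year on study: as written 2 − 1 = +1; annualized 2 − 1/(4/12) = 2 − 3 = −1. The sign reverses.
- Age 12 months or older, two history events, one on study: 2.03 − 2/1.0 = +0.03 under either rule.

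**Step 4: effect on group means.** If 3 of 20 participants are aged 6 months, the overall mean shifts by 3/20 × L × 0.5, which is +0.08, +0.15 and +0.30 per year at L = 1, 2 and 4. In the 0-<2 group the dilution is weaker. With 3 such infants and, say, 3 one-year-olds (an assumption), the shift is 3/6 × L × 0.5, or +0.50 per year at L = 2.

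**Step 5: stability of the corrected rate.** One event at 1 month of age is 12 per year. Suppose three infants aged 1, 6 and 9 months have one event among them, in the youngest. The mean of individual rates is 12/3 = 4 per year. The pooled rate is 1/((1 + 6 + 9)/12) = 0.75 per year.

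**Step 6: the 28-day rule.** SAP 4.1.1.6 ties the discrete count to the adverse event CRF, while the history is collected as PH disease history. The effect if history were counted raw was simulated under Poisson events, with 100,000 participants per rate. An event counted only if it fell more than 28 days after the last counted one.

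| Assumed rate per year | Participants with history events that would merge | Spurious change, history raw | Change, rule applied to both periods |
|---|---|---|---|
| 0.5 | about 2% | −0.02 | 0.00 |
| 1 | about 6% | −0.07 | 0.00 |
| 2 | about 22% | −0.25 | +0.01 |
| 4 | about 56% | −0.88 | +0.03 |

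**The case against.** The strongest reply is that little depends on this. The endpoint is exploratory, nothing is tested, and infants fall in their own age stratum, so the groups aged 2 years and over are untouched. The 12-month counts are summarized at baseline (SAP 4.1.4) and all data are listed, so a careful reader could see the problem. All of that stands, and it limits the consequence. It does not make the rule right: followed as written, it gives a wrong number.

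Two further points also stand. The figure of 3 in 20 is a ceiling, because an infant with no prior event has a baseline of zero under either rule. The protocol puts median symptom onset at 4.5 years, so such infants are plausible. And dividing by a very short history gives unstable rates, so the divisor alone is not a full remedy.

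A reader might go further and infer that the baseline is biased at every age, either because a raw count is set against a rate divided by exposure, or because unmerged history events are set against merged on-study events. The documents do not support this. For about 17 of the 20 planned completers the look-back is a full year and dividing by 1.0 changes nothing. As to merging, nothing in either document says that history is counted raw. Protocol 8.1.3.1 places the screening history, the stone-event definition and the 28-day rule together, and does not limit the rule to on-study events. If history follows that rule, the bias is zero. If it does not, only participants with history events within 28 days of each other are affected.

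**Conclusion.** The baseline rule is wrong as written for participants under 12 months who have at least one prior stone event. Their baseline is understated by a factor of 12 over age in months, which shows as a spurious worsening and works against the drug. The factor is arithmetic and needs no assumption beyond a look-back that starts at birth. The shifts in group means do rest on assumptions: a constant stone rate of 1 to 4 per year, and three infants aged 6 months.

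Infants without a prior event, and all participants aged 12 months or older, are unaffected by the missing divisor. The treatment of concurrent history events is a matter to clarify, not a demonstrated bias. No primary or secondary result changes, but the 0-<2 stone summary should not be reported on the present definition.

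**What to change.** In SAP 4.1.1.2, define the baseline rate as the number of history stone events divided by years of history available, with years = min(365.25 days, age in days at screening)/365.25. Days are safer than completed months, since eligibility starts at birth and a divisor of zero completed months is undefined.

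In SAP 4.4, add total events over total person-years for the history and on-study periods, by age group, so that one very short history does not dominate a mean.

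In SAP 4.1.1.6, name the data source for history events and state that the 28-day rule applies to them where their dates are available.

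The divisor and the pooled rates need only a wording and derivation change, using age at screening and counts already collected. Merging history events needs their dates. The documents do not say that these are recorded, so the cost of that part is uncertain; where dates are missing, the report should say that history was counted unmerged.
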